ANNEX 2. ENCEPP CHECKLIST FOR STUDY PROTOCOLS

Not applicable.

ANNEX 3. ADDITIONAL INFORMATION

1. Physical Functioning Questionnaire (PF-10) based on the 36-Item Short Form Survey.

The following questions are about activities you might do during a typical day. Does your health now limit you in these activities? If so, how much?

Yes, limited a lot	Yes, limited a little	No, not limited at all
▼	▼	▼

- a Vigorous activities, such as running, lifting heavy objects, participating in strenuous sports 1 2 3
- b Moderate activities, such as moving a table, pushing a vacuum cleaner, bowling, or playing golf 1 2 3
- c Lifting or carrying groceries 1 2 3
- d Climbing several flights of stairs 1 2 3
- e Climbing one flight of stairs 1 2 3
- f Bending, kneeling, or stooping 1 2 3
- g Walking more than a mile 1 2 3
- h Walking several hundred yards 1 2 3
- i Walking one hundred yards 1 2 3
- j Bathing or dressing yourself 1 2 3

2. Modified Medical Research Council (mMRC) Questionnaire for Assessing the Severity of Breathlessness

Please circle the number which best describes your grade of breathlessness.

I only get breathless with strenuous exercise. 0

I get short of breath when hurrying on the level or walking up a slight hill. 1

I walk slower than people of the same age on the level because of breathlessness, or have to stop for breath when walking at my own pace on the level. 2

I stop for breath after walking about 100 meters or after a few minutes on level. 3

I am too breathless to leave the house or I am breathless when dressing or undressing. 4

3 Patient Satisfaction Questionnaire

Please choose the number which best describes your satisfaction with Spiolto[®] Respimat[®].

What is your overall satisfaction with the Spiolto[®] Respimat[®] treatment?

1 very dissatisfied 	2 dissatisfied 	3 rather dissatisfied 	4 neither satisfied nor dissatisfied 	5 rather satisfied 	6 satisfied 	7 very satisfied 
--	---	--	---	---	--	---

How satisfied are you with inhaling from the Respimat[®] device?

1 very dissatisfied	2 dissatisfied	3 rather dissatisfied	4 neither satisfied nor dissatisfied	5 rather satisfied	6 satisfied	7 very satisfied
------------------------	-------------------	--------------------------	---	-----------------------	----------------	---------------------

						

2. LIST OF ABBREVIATIONS

Term	Definition / description
AE	Adverse event
BI	Boehringer Ingelheim Pharma GmbH&Co. KG
CR	Complete Response
COPD	Chronic obstructive lung disease
GOLD	Global Initiative for Chronic Obstructive Lung Disease
LABA	Long-acting beta ₂ -adrenoceptor agonist
LAMA	Long-acting anticholinergic bronchodilator
Max	Maximum
MedDRA	Medical Dictionary for Drug Regulatory Activities
Min	Minimum
mMRC	Modified Medical Research Council Scale
NIS	Non-interventional study
PF-10	Physical functioning questionnaire
PGE	Physician's global Evaluation
SAE	Serious Adverse event
TEAE	Treatment-emergent AE
TSAP	Trial Statistical Analysis Plan

3. INTRODUCTION

As per ICH E9^[1], the purpose of this document is to provide a more technical and detailed elaboration of the principal features of the analysis described in the protocol, and to include detailed procedures for executing the statistical analysis of the primary and secondary variables and other data.

This TSAP assumes familiarity with the Clinical Trial Protocol (CTP), including Protocol Amendments. In particular, the TSAP is based on the planned analysis specification as written in CTP Section 9 “Research Methods”. Therefore, TSAP readers may consult the CTP for more background information on the study, e.g., on study objectives, study design and population, treatments, definition of measurements and variables, planning of sample size, randomization.

SAS® Version 9.4 or higher will be used for all analyses.

4. CHANGES IN THE PLANNED ANALYSIS OF THE STUDY

- New analyses set, which is not mentioned in the protocol (Details are displayed in section 6.3):
 - Full analysis set (FAS)

5. ENDPOINT(S)

5.1 PRIMARY ENDPOINT

The primary endpoint of the presented study is “therapeutic success” at visit 2 i.e. approximately 6 weeks after starting treatment, defined as 10-point increase in the PF-10 score between visit 1 and visit 2.

5.2 SECONDARY ENDPOINTS

- Absolute changes in PF-10 score from visit 1 to visit 2
- General condition of the patient, evaluated by the physician (PGE score) at visit 1 and visit 2
- Patient satisfaction with Spiolto® Respimat® at visit 2

5.4 OTHER VARIABLE(S)

Other variables will be baseline characteristics and patient's characteristics such as age, gender, height and weight. Additionally information about concomitant medication, diseases, therapy data, further therapies and comorbidities will be collected as well as about smoking status, exacerbation history, mMRC and GOLD group.

6. GENERAL ANALYSIS DEFINITIONS

6.1 TREATMENT(S)

In the presented study, treatment with Spiolto® Respimat® will be according to product information.

6.2 IMPORTANT PROTOCOL VIOLATIONS

Table 6.2.1 defines the different categories of important protocol violations (PVs). The final column describes which PVs will be used to exclude subjects from the different patient analysis sets^[2].

Table 6.2.1 Important protocol violations

Category/ Code		Description	Requirements	Excluded from
A		Entrance criteria not met		
A1.1		Inclusion criterion 2 (Age >=40 years)	Not met as specified in the protocol	None
A1.2		Inclusion criterion 3 (Patients diagnosed with COPD and requiring long-acting dual bronchodilation (LAMA+LABA) treatment according to approved Spiolto® Respimat® SmPC)	Not met as specified in the protocol	TS, FAS
A2.1		Exclusion criterion 1 (Patients with contraindications according to Spiolto® Respimat® SmPC)	Met as specified in the protocol	None
A2.2		Exclusion criterion 2 (Patients who have been treated with a LABA/LAMA combination (free and fixed dose) in the previous 6 months)	Met as specified in the protocol	None
A2.3		Exclusion criterion 3 (Patients continuing LABA-ICS treatment should not be additionally treated with Spiolto® Respimat® in order to avoid a double dosing of long-acting beta-agonists)	Met as specified in the protocol	None
A2.4		Exclusion criterion 4 (Patients for whom further follow-up is not possible at the enrolling site during the planned study period of approx.. 6 weeks)	Met as specified in the protocol	None
A2.5		Exclusion criterion 5 (Pregnancy and lactation)	Met as specified in the protocol	None
A2.6		Exclusion criterion 6 (Patients currently listed for lung transplantation)	Met as specified in the protocol	None
A2.7		Exclusion criterion 7 (Current participation in any clinical trial or any other non-interventional study of a drug or device)	Met as specified in the protocol	None
B		Informed consent		

Category/ Code	Description	Requirements	Excluded from
B1	Informed consent not available/not done (Inclusion criterion 1)	IC 01 not met as specified in the protocol or informed consent date missing	All

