9.7.3 Planned analyses

All patients who have received at least one dose of Spiolto[®] Respimat[®] will be included in the analysis; this is the treated set. All analyses will be performed on the treated set (as-treated analysis). If patients have missing values for an outcome, those patients will be excluded for that outcome's analysis.

The assessment will be carried out using SAS[®] software. The statistical characteristics presented in the end-of-text tables will be N / mean / SD / min / median / max for continuous variables. Tabulations of relative and absolute frequencies will be presented for categorical variables. Incidence rates and 95% CI will be given when appropriate.

The analyses will relate to the following data as recorded in the eCRF:

- Patient demographics (age, gender, height, and weight)
- Comorbidities
- COPD related and other concomitant medication
- History of smoking
- Reported exacerbations
- Breathlessness based on mMRC score
- Physical Functioning based on PF-10 scores (therapeutic success at visit 2); primary outcome
- Changes from visit 1 to visit 2 in the PF-10 score; secondary outcome
- Patient satisfaction with Spiolto[®] Respimat[®] at visit 2 only; secondary outcome

- General condition of the patient: evaluated by the physician (Physician's Global Evaluation (PGE)); secondary outcome
- Adverse Drug Reactions (ADR & SADR), fatal AEs, pregnancies
- GOLD spirometric classification (1,2, 3, 4)
- GOLD patient groups (A, B, C, D)
- Details of treatment with inhaled respiratory agents before the study
- Details of treatment with respiratory agents during the study
- Reasons for ending treatment during the observation period
- Details of treatment continuation / discontinuation

Main analysis

For the primary outcome, the proportion of patients with therapeutic success will be presented together with the 95% confidence interval.

Further analyses

The patient's general condition (PGE) at visit 1 and visit 2, mMRC at visit 1 and patient satisfaction at visit 2 are categorical variables so they will be analyzed as tabulations of frequencies. Change from visit 1 to visit 2 in the PF-10 score is a continuous outcome, so it will be analyzed with N / mean / SD / min / median / max.

The safety data will be reported according to local requirements.

As similar studies will also be performed in other European countries, data pooling might be considered at the end.

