6.3 PATIENT SETS ANALYSED

Full analysis set (FAS): All screened patients with informed consent, date of registration, at least one documented administration of Spiolto® Respimat® and available PF-10 score at visit 1 and visit 2.

Treated set (TS): All screened patients with informed consent, date of registration and at least one documented administration of Spiolto® Respimat®.

Table 6.3.1 Patient sets analysed

Class of endpoint	Patient set	
	TS	FAS
Primary and secondary endpoints		X
Safety endpoints	X	
Demographic/baseline	X	

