7.1 DEMOGRAPHIC AND OTHER BASELINE CHARACTERISTICS

Only descriptive statistics are planned for this section of the report. All baseline analyses will be done for the treated set.

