7.7 SAFETY ANALYSIS

The analysis of adverse events will be descriptive and conducted according to Boehringer Ingelheim standards. The main focus will be on treatment emergent events. All AE that occurred between start of treatment and 21 days after permanently discontinuation of therapy or end of study will be considered as treatment emergent and will be displayed in frequency tables. Non treatment-emergent events will be assigned to “screening” or “post-treatment” and only be displayed in listings. All analyses will be based on the treated set.

In context of the presented study, only drug-related adverse events or events with fatal outcome (i.e., serious adverse events) will be documented. Their frequency and severity will be tabulated according to MedDRA-SOC and PT. Serious events will be tabulated as well as adverse events (drug-related or serious ones) leading to treatment discontinuation. Moreover, the causality of events with fatal outcome will be displayed.

Unless otherwise specified, the analyses of drug-related adverse events and events with fatal outcome will be descriptive in nature. All analyses will be based on the number of patients with AEs and not on the number of events.

An overall summary of drug-related adverse events and events with fatal outcome will be presented.

[figure not shown]
The frequency of patients with drug-related adverse events or events with fatal outcome will be summarised by primary system organ class and preferred term. Separate tables will be provided for patients with serious adverse events.

The system organ classes will be sorted alphabetically, preferred terms will be sorted by frequency (within system organ class).

For analysis multiple AE occurrence data on the CRF will be collapsed into an AE event provided that all of the following applies:

- All AE attributes are identical (PT, NCI-CTC grade, action taken, therapy required, seriousness, reason for seriousness, relationship, outcome)
- The occurrences were time-overlapping or time-adjacent (time-adjacency of 2 occurrences is given if the second occurrence started on the same day or on the day after the end of the first occurrence). For classification into TEAE or Non-TEAE, the first documented start of event will be used.

For further details on summarization of AE data, please refer to [3] and [4].

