10. HISTORY TABLE

Table 10.1 History table

Version	Date (DD-MMM- YY)	Author	Sections changed	Brief description of change
Draft v0.1	20-JUN-2018		None	This is the first Draft-Version without any modification
Draft v0.2	29-JUN-2018		3, 4, 5.2, 7, 7.4	Minor corrections and added additional analysis (frequency table, normality test) for absolute changes in PF-10 score
Draft v0.3	12-JUL-2018		4, 6.4, 7.3, 7.4	Deleted subgroup analysis
Draft v0.4	13-JUL-2018		6.2, 6.3	Patients who not met inclusion criterion 3 are excluded from all patient analysis sets
Draft v0.5	16-JUL-2018		6.2	Changed 'All' to 'TS, FAS'
Draft v0.6	18-JUL-2018		6.2, 6.3	Changed 'TS, FAS' to 'All' for B1 and changed definition of FAS and TS
Final v1.0	19-JUL-2018		None	This is the first Final-Version without any modification

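### SAP Table 6.2.1 removes dosed patients who fail inclusion criterion 3 from the Treated Set, the only safety population, against Protocol 9.7.3 and without declaring it in SAP section 4

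*SAP*

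**What the plan says.** Protocol 9.7.3 defines the treated set by exposure alone. Patients with at least one dose "will be included in the analysis; this is the treated set. All analyses will be performed on the treated set (as-treated analysis"). The only exclusion it describes is outcome by outcome, for a missing value.

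SAP 6.3 defines the TS as "All screened patients with informed consent, date of registration and at least one documented administration of Spiolto® Respimat". The FAS adds the PF-10 requirement: "at least one documented administration of Spiolto® Respimat® and available PF-10 score at visit 1 and visit 2". Neither definition mentions inclusion criterion 3.

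SAP 6.2 states that the last column of Table 6.2.1 determines who is excluded from which analysis set. Row A1.2, for failure of "Inclusion criterion 3 (Patients diagnosed with COPD and requiring long-acting dual bronchodilation (LAMA+LABA) treatment according to approved Spiolto® Respimat® SmPC"), lists TS and FAS in that column.

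Table 6.3.1 assigns safety endpoints and baseline data to the TS only. SAP 7.7 says "All analyses will be based on the treated set", and SAP 7.1 says "All baseline analyses will be done for the treated set".

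SAP section 4, the list of departures from the protocol, has one entry, the FAS: "New analyses set, which is not mentioned in the protocol". Apart from Table 6.2.1, the rule appears only in the history table, at draft v0.4 of 13 July 2018: "Patients who not met inclusion criterion 3 are excluded from all patient analysis sets".

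**The concern.** A safety population should contain everyone exposed. Row A1.2 takes a group of exposed patients out of the only population used for safety, on an eligibility ground that the protocol does not use to define the set. No other analysis set brings them back.

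The patients removed are those dosed without meeting the criterion tied to the product's approved use. Protocol 11.1 states that adverse reactions may arise from use outside the marketing authorisation, so it treats reactions in such patients as in scope. The SAP would leave them out of the aggregate tables.

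A reader who checks SAP section 4 for departures from the protocol would not learn of this. Section 4 refers the reader to 6.3, which is silent on criterion 3. Two programmers, one working from 6.2 and the other from 6.3, could also reach different denominators. The same row narrows the primary-analysis population in a way that neither 6.3 nor section 4 states.

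**Working it through.** **Comparison of the texts**

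| Place | Who is in the set used for safety |
|---|---|
| Protocol 9.7.3 | Everyone with at least one dose |
| SAP 6.3 | Consent, registration date and at least one documented administration |
| SAP Table 6.2.1, row A1.2 | As in SAP 6.3, less those failing inclusion criterion 3 |
| SAP section 4 | No change to the treated set declared |

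Table 6.2.1 has nine entrance-criterion rows (A1.1, A1.2 and A2.1 to A2.7). Eight list None as the exclusion, including the rows for SmPC contraindications (A2.1) and continuing LABA-ICS (A2.3). Only A1.2 removes anyone, and the SAP gives no reason. Row B1 (no consent) is a separate category and agrees with the consent condition in 6.3.

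The history table lists sections 6.2 and 6.3 as changed at v0.4 and v0.6, and 6.2 at v0.5. Section 4 is not listed in any of the three.

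**The plan's own figures (Protocol 9.5).** With 50% success and n = 372, 0.5 ± 1.96 × √(0.25/372) gives 44.9% to 55.1%, and 372/0.93 = 400. Both reproduce.

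**Size for safety.** The documents give no criterion-3 failure rate and no ADR rate. Assume 400 dosed (the planned size), k = 0 to 20 failures (0 to 5%), 5% ADR risk in the remaining patients and risk r = 0% to 15% in those excluded.

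- Reported rate, on 400 − k patients: 5.0%.
- Rate in all exposed: [0.05 × (400 − k) + r × k] / 400.
- Expected patients with an ADR left out: r × k.

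| k | r | Rate in all exposed | Expected ADR patients left out |
|---|---|---|---|
| 0 | n/a | 5.00% | 0 |
| 8 | 0% | 19.6/400 = 4.90% | 0 |
| 8 | 5% | 20/400 = 5.00% | 0.4 |
| 8 | 15% | 20.8/400 = 5.20% | 1.2 |
| 20 | 0% | 19/400 = 4.75% | 0 |
| 20 | 5% | 20/400 = 5.00% | 1.0 |
| 20 | 15% | 22/400 = 5.50% | 3.0 |

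At r = 5%, the chance of leaving out at least one patient with an ADR is 1 − 0.95^8 = 34% for k = 8 and 1 − 0.95^20 = 64% for k = 20.

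For scale, the 95% interval for 19/380 is 0.05 ± 1.96 × √(0.05 × 0.95/380), or 2.8% to 7.2%. The shift in the rate is well inside that.

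**Size for the primary result.** Assume 19 of 372 scored patients (about 5%) are excluded, with success s in them and 50% in the other 353. The estimate with them included is (0.5 × 353 + s × 19)/372:

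- s = 30%: 182.2/372 = 49.0%
- s = 50%: 50.0%
- s = 70%: 189.8/372 = 51.0%

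Without them it is 50.0%, so the shift is at most 1.0 point. The half-width is 5.1 points at n = 372 and 5.2 points at n = 353.

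**The case against.** **The rule is not hidden.** SAP 6.2 explains what its last column does, and the history table records the edits. This stands: the gap lies in section 4 and 6.3, and nothing suggests concealment. A version log is nevertheless not the place where departures from the protocol are declared.

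**Sections 6.2 and 6.3 can be read together,** one defining the sets and the other listing removals. That is a possible reading, but it does not resolve the conflict with Protocol 9.7.3.

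**The events are not lost.** Protocol 11.2 still requires eCRF entry and an NIS AE form for ADRs and fatal events, and Protocol 9.7.4 requires each removal to be documented with site, patient number and reason. This limits the harm. It does not put the patients back into the aggregate tables, and a duty to document removals does not authorise this one.

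**Leaving such patients out of the efficacy analysis is defensible,** because the objective concerns COPD patients and all analyses are descriptive. This stands. An exclusion limited to the FAS would be acceptable if declared, and showing the primary result both ways is a modest extra.

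**Timing proves little.** Draft v0.4 is dated 163 days after the planned end of data collection (31 January 2018). The actual end is not given, and the whole SAP was drafted after that planned date. No inference of a data-driven choice is warranted.

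**The impact may be nil.** Correct: the number of failures is unknown, and the ADR figures rest on assumed rates.

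**Conclusion.** The concern holds. As written, row A1.2 removes exposed patients from the sole safety population, contradicts Protocol 9.7.3, does not match SAP 6.3 and is not declared in section 4.

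The problem is incomplete counts and an undeclared departure; no large bias is shown. Event counts can only stay the same or fall, while the rate could move either way. With no criterion-3 failures, nothing changes. Under the assumptions above, up to 3 patients with an ADR would be expected to be missing from the tables, the ADR rate would differ by at most 0.5 point and the primary estimate by at most 1.0 point. It should be fixed because the tables would claim to cover the treated patients and might not.

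**What to change.** In Table 6.2.1, row A1.2, change the exclusion from TS and FAS to FAS only, or to None. The TS, and with it every safety and baseline table, then includes each consented, registered patient with at least one documented dose.

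If the FAS exclusion is kept:

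1. Add the criterion-3 condition to the FAS definition in SAP 6.3.
2. Declare it in SAP section 4 as a departure from Protocol 9.7.3.
3. Show the primary result with and without these patients.

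As an optional addition, the same section 4 entry could note that the SAP's TS adds consent, registration date and documented administration to the protocol's one-dose definition.

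The cost is one table cell, one clause in 6.3, one entry in section 4 and one extra row in the primary table. No new data are needed.

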6.3 PATIENT SETS ANALYSED

Full analysis set (FAS): All screened patients with informed consent, date of registration, at least one documented administration of Spiolto® Respimat® and available PF-10 score at visit 1 and visit 2.

Treated set (TS): All screened patients with informed consent, date of registration and at least one documented administration of Spiolto® Respimat®.

Table 6.3.1 Patient sets analysed

Class of endpoint	Patient set	
	TS	FAS
Primary and secondary endpoints		X
Safety endpoints	X	
Demographic/baseline	X	

6.4 SUBGROUPS

Not applicable.

6.5 POOLING OF CENTRES

This section is not applicable because centre/country is not included in the statistical model.

6.6 HANDLING OF MISSING DATA AND OUTLIERS

In context of PF-10 questionnaire, missing values will be replaced with the mean of the other values, if less than half of the questions are missing for a patient. If half or more than half of the questions are missing, no score will be calculated and the PF-10 score will be marked as missing. No other missing data will be imputed.

6.7 BASELINE, TIME WINDOWS AND CALCULATED VISITS

Baseline visit (Visit 1) will include historical and demographic data as well as registration and initial examination. Treatment with Spiolto® Respimat® will be documented at visit 2 after approximately 6 weeks of treatment.

Proprietary confidential information © 2019 Boehringer Ingelheim International GmbH or one or more of its affiliated companies

The mMRC breathlessness scale is completed by the patient at visit 1 and PF-10 questionnaire at visit 1 and 2 as well as satisfaction survey at visit 2. In addition, the PGE is completed by the physician at visit 1 and visit 2.

7. PLANNED ANALYSIS

All analyses in this study are descriptive.

For categorical variables summary tabulations of the number and percentage within each category (with a category for missing data) of the parameter will be presented. For continuous variables number of values, mean, standard deviation, minimum, median, maximum and number of missing values will be presented. Proportion rates and 95% CI will be given when appropriate.

7.1 DEMOGRAPHIC AND OTHER BASELINE CHARACTERISTICS

Only descriptive statistics are planned for this section of the report. All baseline analyses will be done for the treated set.

7.2 CONCOMITANT DISEASES AND MEDICATION

Only descriptive statistics are planned for this section of the report. All analyses will be done for the treated set.

